3.3 Malaria vaccine

A highly effective malaria vaccine remains elusive, but the RTS,S vaccine has progressed through the clinical development stages. RTS,S is a subunit vaccine that includes a portion of the circumsporozoite protein (CSP) co-expressed with Hepatitis B surface antigen combined with AS01 adjuvant. The Phase 3 trial of three doses administered to 5-17-month-olds confirmed moderate protection, with overall efficacy estimates of 50.4% against clinical malaria and 34.8% against severe malaria after three doses (Agnandji, 2011). Efficacy, which waned over time, was marginally improved by boosting at 18 months. The European Medicines Agency adopted a positive scientific opinion of the vaccine for use outside of the European Union. The WHO has created the Malaria Vaccine Implementation Program (MVIP) and selected Malawi as one of the sites to explore the feasibility, efficacy and safety of RTS,S vaccination in the context of routine use. In addition, when exploring RTS,S feasibility and safety in routine health delivery, little evidence exists regarding how RTS,S vaccine may affect *Plasmodium* infection and transmission. An analysis of several RTS,S trials suggested 70-90% protection against microscopy-defined infection (Penny, 2015), but this does not consider submicroscopic, PCR-detected *Plasmodium* infections containing gametocytes infectious to mosquitoes. The significance of our proposed studies is that RTS,S vaccination may reduce human infection prevalence and transmission to mosquitoes. Thus, RTS,S vaccine may offer indirect protection and decrease infection in other age groups. Alternatively, if vaccination permits low-density *Plasmodium* infections that do not lead to disease and treatment-seeking, vaccinees may actually serve as sources of added household transmission. The Malawi Ministry of Health (MOH) has invited our ICEMR to help analyze impacts of RTS,S vaccination on *Plasmodium* transmission and malaria incidence. Knowledge of these outcomes is critical to future role out of the vaccine.

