6.3.2 Sample size

Our sample size estimates are based on previous high and low transmission season surveys conducted during the first ICEMR (2010–2017) in areas similar to the clusters that will be selected for this study. Based on these data, we anticipate that 13%-18% of households will contain a child 7-18 months old. The risk of infection in this age group is estimated to be 21% (30% high and 20% low transmission seasons). In children \leq 10 years of age the risk of infection is estimated to be 31% (46% in the high and 32% in the low transmission seasons). The within-cluster correlation is estimated at 0.004 (0.05 in the high and 0.00 in the low transmission seasons) and 0.14 (0.22 in the high and 0.06 in the low transmission seasons) for children aged 7-18 months and \leq 10 years of age, respectively. Based on these data, by studying the 25 clusters with 20 households with a child 7-18 months per intervention arm, we will analyze 500 children aged 7-18 months and a similar or larger number of older children. For power calculations, we assumed that these proportions represented the risk of incident cases of infection.

This proposed sample size will allow us to estimate moderate effectiveness of the combined interventions (versus no intervention) with 80% power in 2-sided tests, accounting for within-cluster correlation, and with α -level of 0.05. For instance, based on the cross-sectional estimations of individual risk of malaria infection obtained at enrollment of each cohort, we will be able to

detect the effectiveness of 34% (36% and 33% when stratifying by season) in children 7-18 month-old (Hayes, 2009). In a repeated measure analysis, with within-subject correlation of 1.5 to 2 times larger than within-cluster correlation, we will be able to detect effectiveness of 34-37% in children 7-18 month old (Liu, 2002).

For entomological assessments, 100 households from each of the two arms will be visited for entomological analysis including *Anopheles* abundance, female mosquito parity, and source of blood meal and sporozoite prevalence. Based on our previous experience, we have found an average of one *Anopheles* mosquito per household sampled (although with very heterogeneous distribution), and 75-95% human-biting prevalence.

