At enrollment, we will conduct household and individual interviews. In this initial household interview, we will collect data on hemoglobin status, SES, household construction, and on ITN use (PBO or conventional net). Through visual inspection of each bed net to determine if it is a PBO or conventional net, we will also identify which other household members aged ≤ 10 years of age who slept under each bed net and with respective frequency. We will also document vaccination status including RTS,S vaccine administrations. See details of proposed study procedures at the enrollment and every two months follow up for six months in the community. See Table 3 above.

Individual participant's visits. Every two months through the sixth month, participants in the cohort will be invited to the nearest central location for data and specimen collection. A structured questionnaire will be administered to collect information on demographics, net utilization and vaccination status). At each visit, we will review the target child's health passport to document all vaccinations, including the standard EPI vaccines through 9 months of age and the 15-month measles vaccine. We will also document the dates of all RTS,S vaccine administrations.

Human blood samples and testing.

Clinical testing: To establish the study cohort, potential participants will be screened by the study team to assess for their eligibility. At enrollment the cohort will be screened for malaria using Malaria Rapid Diagnostic Tests (The SD BIOLINE Malaria Ag P.f/Pan (HRP-II)™ rapid diagnostic test RDT) and those participants who test positive will be treated with a full, weight appropriate treatment course of dispersible artemether-lumefantrine (LA) by government Staff. The RDT and treatment of RDT positive children will be repeated at the final visit.

Hemoglobin levels from each participant will also be examined at enrollment and at every two-month follow-up visits. Parents of children with a haemoglobin level under 11 g/dl will be advised to take the child to a health facility for follow-up care and will be given a referral letter with the haemoglobin reading to show to staff at the health facility by the research Team.

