6.5 Analysis Plan

To describe the study population, evaluate potential confounding, and identify sources of selection bias, baseline information will be summarized and compared across children who do/do not comply with either RTS,S vaccination, or with PBO nets, or with both. These analyses will be primarily conducted at an individual level, but to assess robustness of results, comparisons will also be conducted at cluster levels. Analysis at individual levels will be performed using random-effect models to account for the within subject correlation. Linear, logistic, and over-dispersed Poisson models will be used to analyze continuous, categorical, and count variables, respectively. Baseline information will also be assessed for children ≤10 years old at individual- and household-level through nested random effects accounting for correlation of subjects within households.

For analysis of effectiveness on prevalence and transmission, separate models will be fitted to estimate total and direct effectiveness (Hayes, 2009; Hallaron, 2010) in children aged 7-18 months at six time points. Analysis will be primarily done at the individual level, with intervention

groups compared through nested random effect models (accounting for correlation across time). A subgroup analysis will include children who will have been vaccinated within 3 months from Month (M) 1. Models will be logistic for the occurrence of infection and presence of gametocytes, and overdispersed Poisson or zero-inflated for gametocyte density. In all analysis, the linearity of association of the outcome with predictors will be evaluated through semiparametric regression and, if necessary, predictors will be categorized or transformed. In secondary analyses, all incident events will be assessed in individual-level analysis through negative binomial models (corresponding to discrete proportional hazard multiple event models) with nested random effects. We will also explore comparisons of the number of new infection events per follow-up month in over-dispersed Poisson models. Since adherence to vaccination (post-randomization variable) can introduce selection bias, we will also explore estimating total and direct effectiveness using causal inference models.

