7.3.2 Known Potential Benefits

This study will enroll children aged 7 months to 10 years within two government HC catchment areas. In Malawi, this age group is at greatest risk of malaria infection and its complications. The participants will benefit from being intensively followed-up during the six months specifically at (0, 2, 4, and 6 months) study period, and by having mRDT results provided and treatment provided, if indicated at 1 and 6 months. The research team will give the participants health advice and refer them for treatment at the local health center. The study team will support the local health center with laboratory services and drugs so that all participants will be guaranteed access to laboratory diagnostics of malaria and or antimalarial treatment where necessary. The individuals who participate in this study will have access to prompt diagnosis and treatment of malaria when appropriate. We are

going to perform mRTDs to participants at recruitment and 6 months. Similarly, we will also test participants for anemia at recruitment and at all the follow up months. By participating in this study, the children will have access to high-quality and personalized medical attention. In the case of life-threatening emergencies, the study team will use their vehicle to transfer the study participants to the nearest government or private hospital. The minimal risks of this study, associated with finger pricks and the breaches of confidentiality are outweighed by these benefits. In addition, the study will provide support to the health centre in the study with resources mainly in malaria diagnosis and treatment which will benefit the community at large, not just research participants. In addition, the results of this study will help to maximize the implementation and impact of malaria prevention and control measures throughout Malawi. Each enrolled household will be given K2000 for each study visit as compensation for their transport cost during enrolment and monthly visits.

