9 REQUIREMENTS

For the evaluations of study participants, each study site will have the regular HC-based team and field teams. The regular HC teams will be comprised of government employed clinical, nursing and laboratory staff, and ICEMR-employed epidemiological field teams of a nurse, enumerator and a village field assistant. The study nurses and enumerators will receive training in human subjects' research, entomological sampling, and data collection using electronic data capture devices. The HC based team will be responsible for passive disease surveillance from participants referred by the field teams during monthly visits and/or from participant's non-scheduled visits to the facilities at any other time during the follow-up. Responsibilities assigned to the study team members will be stipulated in standard operating procedures (SOPs) and will be conducting in-depth interviews. Entomological assessments will be conducted by a different team comprised of an entomology research assistants and field technicians.

A data team lead by Data Managers will be responsible for receiving, archiving and processing all incoming data according to standard operating procedures for local storage and transfer to collaborating institutions. All data will be collected using electronic devices. The nurse, enumerator and an entomology research assistant will be using laptop computers to access the REDCap electronic data capture system for data collection. The REDCap system will be accessed using the internet, however, if internet connectivity is lost, an offline version of REDCap installed on the laptops will be used. The field worker will use the tablet computer to collect data.

Other requirements include local transportation (a vehicle, motorcycles, and bicycles will be procured), office administration (computers, office supplies, space rentals), laboratory and pharmaceutical consumables, including kits for Luminex assays and calibration reagents for the Luminex machine in the laboratory of Malawi, and protective wear. Details are highlighted in the budget below.

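### Malaria treated between two-monthly visits is not described as recorded or linked to the infection outcome, so the incidence analyses miss cleared infections and can be biased either way if treatment differs by arm

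*Combined protocol and SAP*

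**What the plan says.** Section 6.4 describes the two-monthly interview: "A structured questionnaire will be administered to collect information on demographics, net utilization and vaccination status". The health passport is reviewed at each visit, but for the target child and for vaccinations. Table 3 has no row for illness or antimalarial use since the previous visit, and Table 1 lists no clinic-episode data source.

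Infection is assessed by quantitative PCR on the finger-prick samples. Section 6.5 states: "Models will be logistic for the occurrence of infection and presence of gametocytes". It gives no covariate, censoring or outcome rule for treatment between visits. It also plans secondary models of all incident events and of new infections per month of follow-up, without defining an event or naming its source.

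Treatment between visits is nevertheless expected. Section 7.3.2 promises that "all participants will be guaranteed access to laboratory diagnostics of malaria and or antimalarial treatment where necessary". Section 7.3.1 has participants checked for disease when they come to the health centre ill, and section 9 says: "The HC based team will be responsible for passive disease surveillance from participants referred by the field teams". Nothing connects that surveillance to the outcomes in 6.5.

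**The concern.** A child who is infected, treated and cleared between two samples is PCR-negative at the next visit. For prevalence that is correct. For an incidence analysis it is a missed event. Section 6.3.2 also assumes that its cross-sectional proportions stand for incident risk, which they do not if many infections are removed by treatment.

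Two consecutive positive samples raise a second problem. Without treatment dates they cannot be classed as one persisting infection or as a cure followed by reinfection, so a count of new infections has no firm basis.

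Each arm is a single health centre (Nyambi or Kalembo), so any difference in clinic use, testing or drug supply is also a difference between arms. Section 3.3 raises a further route by which treatment could differ: vaccination might permit low-density "infections that do not lead to disease and treatment-seeking, vaccinees may actually serve as sources of added household transmission". Older children in the household, who carry the indirect-effectiveness analysis, have no passport review described at all.

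**Working it through.** **1. The plan's own figure.** Section 6.3.2 sizes the study "by studying the 25 clusters with 20 households with a child 7-18 months per intervention arm", that is 25 × 20 = 500 children, "with 80% power in 2-sided tests, accounting for within-cluster correlation, and with α -level of 0.05". The control risk is given as: "The risk of infection in this age group is estimated to be 21% (30% high and 20% low transmission seasons"). The stated within-cluster correlation is 0.004 overall.

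- Design effect = 1 + (20 − 1) × 0.004 = 1.076; effective n = 500 / 1.076 = 464.7 per arm.
- Risks at 34% effectiveness: 21% v 21% × 0.66 = 13.86%.
- Power of the two-proportion test = 82%. The 34% reproduces.

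**2. Missed infections counted as events.** Let f0 and f1 be the shares of infections treated and cleared before the next sample in the control and intervention arms. Counted risk = true risk × (1 − f), and effectiveness = 1 − 0.66 × (1 − f1)/(1 − f0).

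| f0 / f1 | Counted risks | Effectiveness | Power |
|---|---|---|---|
| 0 / 0 | 21.0% v 13.9% | 34% | 82% |
| 30% / 30% | 14.7% v 9.7% | 34% | 64% |
| 20% / 10% | 16.8% v 12.5% | 26% | 46% |
| 30% / 20% | 14.7% v 11.1% | 25% | 38% |
| 10% / 20% | 18.9% v 11.1% | 41% | 92% |

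Equal shares leave the risk ratio unchanged and cost only power. On the odds-ratio scale of the planned logistic models they move the estimate slightly, from 39.5% to 37.7% at 30% / 30%. The planning risks are cross-sectional and may already be net of routine treatment, so these power losses may be overstated.

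**3. Visit prevalence.** Suppose the intervention lowers the force of infection by 34%. At steady state, if treated infections clear at once and post-treatment protection is ignored, prevalence odds = force of infection × duration × (1 − f). So intervention odds = control odds × 0.66 × (1 − f1)/(1 − f0), and duration cancels. Control odds are 0.20/0.80 = 0.25 at 20% prevalence and 0.30/0.70 = 0.4286 at 30%.

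| f0 / f1 | Intervention odds (control 20%) | Prevalence | Effectiveness, control 20% | Effectiveness, control 30% |
|---|---|---|---|---|
| equal, including 0 / 0 | 0.165 | 14.2% | 29.2% | 26.5% |
| 30% / 20% | 0.189 | 15.9% | 20.7% | 18.6% |
| 30% / 15% | 0.200 | 16.7% | 16.5% | 14.8% |
| 20% / 30% | 0.144 | 12.6% | 36.9% | 33.9% |

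The step from 34% to 29% occurs with no treatment at all: prevalence saturates, so it is not a treatment effect.

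Time-dependent versions follow the cohort to months 2, 4 and 6 after treatment of test-positives at enrolment. They assume 4-month untreated infections, a rapid test that finds 60% of infections, and two weeks of post-treatment protection. At 20% control prevalence they give about 30%, 20–22%, 15–18% and 36–39% for the four rows. A two-week delay to treatment raises the second and third to about 23% and 19%.

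**4. The composite.** Counting a child as infected if PCR-positive at the visit or treated for confirmed malaria since the last one gives about 27–32% in those versions, and about 25% at the lowest if enrolment treatment is left out of the model. It is more stable than prevalence when shares differ, but does not recover 34% either.

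**5. Direction.** Take the treated share as proportional to clinical cases per infection, and section 3.3's 50.4% protection against clinical malaria. If infections fall by 34%, a 30% treated share becomes 30% × 0.496/0.66 = 22.5% in vaccinees, which biases toward no effect. If infections fall by 70%, the low end of the range section 3.3 gives for microscopy-defined infection, it becomes 30% × 0.496/0.30 = 49.6%, which biases upward. Section 3.3 notes that this range leaves out submicroscopic infection, so the sign stays open.

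**The case against.** The stated outcomes are infection prevalence, gametocyte prevalence and entomological measures. A cured child is correctly negative for prevalence, and carriage of untreated low-density infections is what PCR and gametocyte prevalence measure directly. Exposure serology is also planned (sections 6.4 and 6.5) and does not depend on parasites being present on the visit day. Passive surveillance is planned, and the questionnaire itself is not in the documents, so it may hold more items than the text lists. All of this stands. It limits the point to the incidence analyses, to the reading of prevalence as incident risk, and to comparisons in which treatment differs by arm.

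A reader might infer that treatment is ignored altogether and that cured control infections hide the true effect. The documents do not support that. Surveillance is described; what is missing is its link to the outcome. Missed infections arise in both arms, and section 3.3 offers differential treatment-seeking only as a possibility. Nor does it follow that the study cannot address the low-density carriage question.

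A composite built on clinic records has its own weakness: clinic access, stock and record-keeping may differ between the two health centres and cannot be separated from arm. That rules it out as a replacement for prevalence, but not as a sensitivity analysis.

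**Conclusion.** The point holds as a cheap improvement. As described, the plan records no malaria or antimalarial treatment between visits and does not link clinic-detected episodes to infection. Its incidence analyses would therefore miss treated infections and could not separate persistence from reinfection. Visit prevalence stands as prevalence.

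Bias in the comparison requires unequal treated shares: toward no effect if control infections are treated more, upward if intervention-arm infections are. The documents settle neither the sign nor the size. Differences of 10 to 15 percentage points in treated share move visit-prevalence effectiveness from about 30% to between roughly 15% and 39%. That rests on assumed values for the treated shares, infection duration, test sensitivity and post-treatment protection. A near-total loss of the effect is not supported in these scenarios.

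**What to change.** - At each two-monthly visit, extract from the health passport and the health-centre record every malaria test result and antimalarial course since the last visit, with dates, for all enrolled children including the older household children.
- In section 6.5, define an incident event and a new infection from these data, including how consecutive positives with and without intervening treatment are classed.
- Report the treated proportion by arm, and the enrolment sample separately from follow-up samples.
- Keep visit prevalence as the main outcome. Add PCR-positive at the visit or treated confirmed malaria since the previous visit as a sensitivity analysis, read alongside the serology.
- Reconcile the visit schedule on which the intervals depend: sections 7.3.1, 7.3.2 and 9 refer to monthly visits where section 6.4 has two-monthly ones, and section 6.5 refers to six time points for the target children against four visits each.

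The cost is a few form fields, passport review for the older children, a clinic-record extraction and one more outcome in models already planned. Records may be incomplete, and their quality may differ by health centre and hence by arm, so the composite can carry ascertainment bias of its own. Dated treatment histories may be hard to recover if not collected during follow-up.

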6.5 Analysis Plan

To describe the study population, evaluate potential confounding, and identify sources of selection bias, baseline information will be summarized and compared across children who do/do not comply with either RTS,S vaccination, or with PBO nets, or with both. These analyses will be primarily conducted at an individual level, but to assess robustness of results, comparisons will also be conducted at cluster levels. Analysis at individual levels will be performed using random-effect models to account for the within subject correlation. Linear, logistic, and over-dispersed Poisson models will be used to analyze continuous, categorical, and count variables, respectively. Baseline information will also be assessed for children ≤10 years old at individual- and household-level through nested random effects accounting for correlation of subjects within households.

For analysis of effectiveness on prevalence and transmission, separate models will be fitted to estimate total and direct effectiveness (Hayes, 2009; Hallaron, 2010) in children aged 7-18 months at six time points. Analysis will be primarily done at the individual level, with intervention

groups compared through nested random effect models (accounting for correlation across time). A subgroup analysis will include children who will have been vaccinated within 3 months from Month (M) 1. Models will be logistic for the occurrence of infection and presence of gametocytes, and overdispersed Poisson or zero-inflated for gametocyte density. In all analysis, the linearity of association of the outcome with predictors will be evaluated through semiparametric regression and, if necessary, predictors will be categorized or transformed. In secondary analyses, all incident events will be assessed in individual-level analysis through negative binomial models (corresponding to discrete proportional hazard multiple event models) with nested random effects. We will also explore comparisons of the number of new infection events per follow-up month in over-dispersed Poisson models. Since adherence to vaccination (post-randomization variable) can introduce selection bias, we will also explore estimating total and direct effectiveness using causal inference models.

To examine antibodies of exposure, two approaches will evaluate the association between levels of exposure antibodies and intervention groups: 1) antibody levels will be summarized using partial least square regression (PLS); 2) levels of individual antibodies will be used. Summary scores and antibody levels will be compared over time between the two groups through joint outcome (shared parameter) models (Verbeke, 2010). Moreover, joint outcome models will be fit for positivity of responses and a zero-inflated model will be fit for the breadth of responses (number of antibodies that are positive in a subject).

For analysis of effectiveness in all household members (in Phase 1, children aged >18 months and \leq 10 years old), indirect effectiveness at the individual level at four-time points will be estimated. Also, in nested random effect models for individual analysis, we will account for correlation across visits, within the household. The household-level analysis will be conducted by summarizing outcomes in the household, and also in nested random effect models, using the same link functions described above.

For entomological outcomes, analysis of effectiveness will be performed comparing intervention groups through zero inflated negative binomial models with random effects, including as offsets hours of capture effort or number of captured mosquitoes, as appropriate. Outcome variables will include abundance of *Anopheles*, sporozoite rates, blood-meal originated from humans, and female parity in households.

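### The sample size counts within-cluster correlation, but the human effectiveness models in 6.5 name only visits and household, so standard errors for older children and the high season may be too small

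*Combined protocol and SAP*

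**What the plan says.** **Sizing (6.3.2).** The design is reached "by studying the 25 clusters with 20 households with a child 7-18 months per intervention arm", and power is claimed "with 80% power in 2-sided tests, accounting for within-cluster correlation". For children aged 7-18 months, "The within-cluster correlation is estimated at 0.004 (0.05 in the high and 0.00 in the low transmission seasons"; for children up to 10 years the corresponding figures are "0.14 (0.22 in the high and 0.06 in the low transmission seasons". On numbers, "we will analyze 500 children aged 7-18 months and a similar or larger number of older children".

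**Analysis (6.5).** For effectiveness in children aged 7-18 months, intervention "groups compared through nested random effect models (accounting for correlation across time". For the older household children, "in nested random effect models for individual analysis, we will account for correlation across visits, within the household". The one mention of cluster is in the paragraph on baseline description: "to assess robustness of results, comparisons will also be conducted at cluster levels". The incident-event, antibody and entomology models include or imply random effects but do not list their levels.

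**The cluster unit.** It is not defined. Table 3 refers to predetermined clusters found with satellite imagery, section 6.6 speaks of villages or clusters when describing maps, and section 6.4 recruits from health-centre registers and traces children back to their homes.

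**The concern.** The sizing and the analysis of the same study use different correlation structures. All children in a cluster have the same intervention status, so correlation between them adds directly to the variance of the comparison between arms. A model with only child and household effects leaves that part out, and its standard errors are too small wherever the within-cluster correlation is not close to zero.

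The consequence is a false positive. Section 6.1 makes the application for the larger study depend on significant results here, and Table 2 schedules a Go/No-Go assessment on these data. Understated standard errors push that decision towards go.

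**Working it through.** **Inputs, all from 6.3.2.** 25 clusters per arm and 20 children per cluster (m = 20); two-sided alpha 0.05; 80% power. For 7-18 months, risk is 21% overall, 30% high season, 20% low season, with correlation (ICC) 0.004, 0.05, 0.00. For children up to 10 years, risk is 31%, 46%, 32%, with ICC 0.14, 0.22, 0.06. I apply the last set to children over 18 months, because the plan gives no other.

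**Step 1. Reproduce the plan's detectable effects.** Two-proportion test with effective n per arm = 500 / (1 + 19 × ICC).

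| 7-18 months | Effective n | Stated effect | Power at it | Effect giving 80% |
|---|---|---|---|---|
| Overall | 500/1.076 = 465 | 34% | 81.9% | 33.2% |
| High season | 500/1.95 = 256 | 36% | 81.2% | 35.5% |
| Low season | 500/1.00 = 500 | 33% | 80.0% | 33.0% |

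The plan's figures reproduce with clustering counted. Without it, the high-season figure would be about 26%. The overall figure needs ICC 0.004; at 0.04 it would be about 42%.

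**Step 2. Error when cluster is left out.** At one visit with one child per household, visit and household terms absorb none of the cluster correlation. The ratio of true to fitted variance is R = 1 + (m − 1) × ICC, and the actual error of a nominal 5% test is 2 × [1 − Φ(1.96/√R)]. The catchments are taken not to differ otherwise.

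| Group | ICC | R (m = 20) | Error | Simulated |
|---|---|---|---|---|
| 7-18 months, low | 0.00 | 1.00 | 5.0% | 4.9% |
| 7-18 months, overall | 0.004 | 1.076 | 5.9% | 5.7% |
| 7-18 months, high | 0.05 | 1.95 | 16.0% | 16.3% |
| Older, low | 0.06 | 2.14 | 18.0% | 18.1% |
| Older, overall | 0.14 | 3.66 | 30.6% | 30.1% |
| Older, high | 0.22 | 5.18 | 38.9% | 39.2% |

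Example: for older children overall, 1.96/√3.66 = 1.02, giving 30.6%. The simulation drew beta-binomial clusters, 25 per arm, 40,000 runs, with no arm difference. The formula does not involve prevalence.

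**Step 3. Sensitivity.**
- *Smaller clusters.* Section 6.4 expects about 260 vaccinated children in Nyambi; 260/25 = 10.4 per cluster. If that held in both arms and both age groups (an assumption), the errors would be 5.0%, 5.4% and 11% for 7-18 months (low, overall, high) and 12%, 20% and 26% for older children.
- *Two older children per household.* With 40 per cluster, a household term fitted and household correlation equal to the ICC, R = (1 + 39 × ICC)/(1 + ICC). The errors are 27%, 41% and 48%.
- *Four visits pooled.* With within-child correlation 1.5 to 2 times the ICC (the plan's range) and cluster effects that persist over visits (an assumption), the 7-18 month errors are about 8.5% overall and 32-33% in the high season.

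**Step 4. Does a cluster term repair it?** A t-test on cluster proportions with 48 degrees of freedom gave 4.7-5.1% error in all six settings. A logistic model with a cluster random intercept and 48 degrees of freedom gave 3-6% (1,000 runs).

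**Step 5. Detectable effect in older children, which the plan does not state.** Step 1's method with 500 per arm gives 46% overall, 42% high season and 36% low season. The overall value uses the stated 31% risk, which lies below both seasonal values (46% and 32%). At their midpoint, (46 + 32)/2 = 39%, it is about 40%. Power for a 34% effect is 51%, 61% and 76%.

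**The case against.** **The word *nested* may already include cluster.** With about one child aged 7-18 months per household, visits within child is a single grouping level, so *nested* hints at something above it. Section 6.5 cites a cluster-randomised-trials textbook for these models, and the repeated-measures power in 6.3.2 uses both within-subject and within-cluster correlation. This may well be what was meant. No human effectiveness model says so, however, and an analyst following the text as worded would fit child and household. That is why the error rates are conditional.

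**The only powered comparison is barely touched.** This is true for 7-18 months overall and in the low season at a single visit. The material cases are the high-season comparison, for which the plan also states a detectable effect, and the indirect effect in older children, which 6.3.1 describes as preliminary.

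**The catchments do differ.** Section 6.2 gives 2015 incidence of 367 per 1,000 in Machinga and 310 in Balaka, a ratio of 1.18. If that ratio carried over to prevalence and the interventions did nothing, a correctly clustered test would still reject about 29% of the time (7-18 months overall), 27% (7-18 months, high season) and 17% (older, overall), in the direction against the intervention. This stands: a cluster term cannot separate intervention from district. It is a second problem and does not excuse the first.

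**Transfer of the correlations.** They come from earlier surveys in similar areas. Whether they hold for clusters inside one health-centre catchment is not known, so the sizes are indicative. The 10.4 scenario is also only illustrative, because 260 is a count at one date before recruitment starts.

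**Conclusion.** The concern holds. Section 6.3.2 relies on within-cluster correlation, and no human effectiveness model in 6.5 names it. A robustness comparison at cluster level, even if it were extended to effectiveness, would not correct the primary models.

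If the models are fitted with the named levels only, the effect is negligible for 7-18 months overall and in the low season at one visit (5-6%). It is material for that group in the high season (16%) and large for older children (18-39%). The figures rest on 20 children per cluster, one visit, the plan's correlations carried over to these clusters and to the group over 18 months, and catchments that do not otherwise differ. With two older children per household the error would be higher; with smaller clusters it would be lower but still 11-26% in the affected comparisons. For the incident-event, antibody and entomology models the plan is under-specified, and nothing more can be concluded. This should be fixed before the data are analysed.

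**What to change.** In 6.5:

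1. Define the cluster unit used in 6.3.2 and make sure each child can be linked to it, by a recorded field or from household GPS.
2. Add a random intercept for cluster, above household and child, to the human effectiveness models, with degrees of freedom based on the number of clusters (48 for 25 per arm). For 7-18 months the household and child levels nearly coincide, so one of them can be dropped.
3. Name a cluster-level summary analysis of effectiveness as the check on those models.
4. List the random-effect levels of the incident-event, antibody and entomology models.
5. State the detectable effect for older children and resolve the overall risk that it uses.
6. Say plainly that the cluster term covers only variation between clusters within an arm, and that with one catchment per arm the comparison stays confounded with district.

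The cost is a definition, a linkage field and analysis wording. Intervals become wider. The stated 34%, 36% and 33% already allow for this at 20 per cluster, so they need not change. Register-based recruitment does not guarantee 20 per cluster, so achieved cluster sizes should be reported.
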